14.3 Stratification Factors

Patients will be stratified based on enrolling institution.

Blocked randomization will be performed at all participating sites. A series of randomized blocks will be generated for each participating site with a 1:1 allocation ratio. This will provide assurance that there will be an equal patient allocation to both treatment arms at any given participating site.

14.4 Analysis of Secondary Endpoints

Secondary endpoints include objective response rate (CR+PR) and complete response rate (CR) (estimated via binomial proportions), and Kaplan-Meier overall survival. Overall survival will be defined as the time from randomization day until death. Ninety-five percent confidence intervals will be calculated for the objective response proportion in each group via binomial proportions. Comparison of the objective response rate and complete response rate between the treatment groups will be performed by the chi-square test. The comparison of the overall survival distributions between the treatment groups will be performed by the log-rank test. Analysis of these three secondary endpoints will

be considered hypothesis-generating only and will be adjusted for multiplicity of outcomes by the Bonferroni method. In the event that no significant result is observed for the primary endpoint (PFS), significant findings for the secondary endpoints (even after correction for multiplicity of outcomes) will not result in efficacy claims for labeling purposes. Similarly, if a significant finding is observed for the primary endpoint, significant findings for the secondary endpoints will still not result in efficacy claims for labeling purposes. All other secondary endpoints (i.e., event-free survival, duration of response, time to progression, progression-free survival 2, and quality of life measures) will only be descriptively presented for each treatment group and no formal statistical comparison will be made between treatment arms. Confidence intervals for the secondary endpoints of objective response rate, complete response rate, and overall survival will be Bonferroni-corrected. The frequency of subjects experiencing toxicities will be tabulated. Toxicities will be assessed and graded according to CTCAE v. 4.0 terminology. Exact 95% confidence intervals around the toxicity proportions will be calculated to assess the precision of the obtained estimates.

All p-values will be two-sided with statistical significance evaluated at the 0.05 alpha level. P-values will be Bonferroni-corrected for the secondary endpoints of objective response rate, complete response rate, and overall survival. All analyses will be performed in SAS Version 9.4 (SAS Institute, Inc. Cary, NC) and Stata Version 14.0 (StataCorp, College Station, TX).

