3.8 Rationale for BiRD Combination in Multiple Myeloma

While new anti-myeloma therapies such as bortezomib and immunomodulatory drugs have been developed, multiple myeloma remains an incurable malignancy. Given that obtaining a complete remission with therapy will allow patients with newly diagnosed multiple myeloma to enjoy a higher quality of life and longer duration of freedom from disease symptoms, finding an optimally effective and well-tolerated regimen is imperative.

Based on the immunodulatory effect of biaxin, the unique anti-myeloma activity of lenalidomide, and the synergistic properties of dexamethasone, the combination of BiRd has demonstrated to be highly effective in the treatment of multiple myeloma, and is anticipated to provide superior outcomes when compared to lenalidomide and dexamethasone therapy alone. A phase II study of clarithromycin (500mg twice daily), lenalidomide (25mg daily for 21 days out of a 28 day cycle), and low dose dexamethasone (40mg weekly) called the BiRd regimen was conducted.³⁰ By replacing thalidomide with lenalidomide into our former BLTD treatment platform, we achieved an overall response rate of 90.3%, and a higher CR rate compared with the earlier BLTD data, 30% vs. 13%. Retrospective case matched analysis comparing patients induced with BiRd vs Rd found that the addition of clarithromycin to Rd significantly increased patient's rate of response, with 90.3% vs 79.1% of patients achieving PR or greater, and 45.8% vs 13.9% of patients achieving CR.³¹ While promising, randomized phase III studies are needed to confirm the superiority of BiRd compared with RD in terms of response rates and survival.

This study is intended to investigate the efficacy of combination therapy with an induction phase utilizing a combination clarithromycin (Biaxin[®]), lenalidomide (Revlimid[®]), dexamethasone (Decadron[®]), in multiple myeloma patients who are newly diagnosed and require treatment when compared to patients who receive lenalidomide

and dexamethasone alone. Randomized phase III studies are needed to confirm the superiority of BiRd compared with Rd in terms of response rates and survival. We anticipate the addition of lenalidomide and bixin will lead to a greater CR rate, shorter times to response, and less toxicity. The primary endpoints of this trial include best response rate, toxicities, progression free survival, event free survival, and overall survival.

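### Section 14.4 adjusts ORR, CR and OS by plain Bonferroni; Holm's step-down would hold the same family-wise error with some more power, at almost no cost

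*Combined protocol and SAP*

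**What the plan says.** Section 14.4 formally tests three secondary endpoints: ORR and CR by chi-square and OS by log-rank. On level and adjustment it states:

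- "All p-values will be two-sided with statistical significance evaluated at the 0.05 alpha level".
- The three analyses will "be considered hypothesis-generating only and will be adjusted for multiplicity of outcomes by the Bonferroni method", and again: "P-values will be Bonferroni-corrected for the secondary endpoints of objective response rate, complete response rate, and overall survival".
- "Confidence intervals for the secondary endpoints of objective response rate, complete response rate, and overall survival will be Bonferroni-corrected".
- Even if PFS is positive, "significant findings for the secondary endpoints will still not result in efficacy claims for labeling purposes".

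All other secondary endpoints are descriptive. No step-down or other sequential procedure is named. The divided level is not printed; with three tests it is 0.05/3 = 0.0167.

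Section 14 assumes no response rate, number of deaths or OS effect, and states no power for these endpoints. The only BiRd versus Rd response rates are in section 3.8, from a retrospective case-matched comparison: "90.3% vs 79.1% of patients achieving PR or greater, and 45.8% vs 13.9% of patients achieving CR". The same section reports a 30% CR rate for BiRd in a single-arm phase II study.

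**The concern.** Bonferroni holds each of the three tests at 0.0167 whatever the other two show. Holm compares the smallest p-value with 0.05/3, the next with 0.05/2 and the largest with 0.05, stopping at the first failure. Once one endpoint is significant, the next is tested at 0.025 at no cost in family-wise error.

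Comparing ORR and OS between arms is a stated objective (2.1.3 and 2.1.4), and the sponsor chose formal adjusted tests for just these three endpoints. A less powerful adjustment makes it somewhat more likely that a real ORR or OS difference is reported as not significant. What is at stake is how these secondary comparisons are described, not the primary result.

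**Working it through.** **1. The plan's own figure.** The plan gives power for PFS only: 133 events, hazard ratio 1.75, 90% power, two-sided 0.05 (section 14.2). Schoenfeld's formula gives 4(1.960 + 1.282)²/(ln 1.75)² = 134.2 events. Power at 133 events is Φ(√133/2 × ln 1.75 − 1.960) = Φ(3.227 − 1.960) = 0.897. The design reproduces closely.

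**2. Inputs for the secondary tests.**
- 153 per arm (section 14.2).
- ORR 90.3% v 79.1%; CR 45.8% v 13.9%; alternative BiRd CR 30% (section 3.8).
- BiRd CR 20%: assumed, as a pessimistic case.
- OS: 60 to 118 deaths, hazard ratio 0.65 to 0.75 (BiRd over Rd): assumed, since the plan gives neither.

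**3. Single-test power.** For two proportions, power = Φ{[d√n − z√(2p̄(1−p̄))]/√(p₁(1−p₁)+p₂(1−p₂))}. For ORR, d = 0.112 and p̄ = 0.847, so d√n = 1.385, √(2p̄(1−p̄)) = 0.509 and the denominator is 0.503.

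| Level | z | ORR power |
|---|---|---|
| 0.0167 | 2.394 | 0.630 |
| 0.025 | 2.241 | 0.686 |
| 0.05 | 1.960 | 0.780 |

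CR power at 0.0167, against 13.9%, is above 0.999 if BiRd CR is 45.8%, 0.85 at 30% and 0.16 at 20%.

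For OS, power = Φ(√D/2 × ln(1/HR) − z). With 118 deaths and HR 0.75 this is Φ(1.563 − 2.394) = 0.20 at 0.0167.

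**4. Bonferroni against Holm.** Simulation, 200,000 trials per row: multinomial responses with CR counted within ORR, chi-square tests, and a normal OS log-rank statistic independent of response. ORR power under Bonferroni is 64% in every row.

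| BiRd CR | OS scenario (assumed) | ORR, Holm | OS, Bonferroni → Holm |
|---|---|---|---|
| 45.8% | no effect | 69% | – |
| 45.8% | HR 0.75, 60 deaths | 70% | 10% → 18% |
| 45.8% | HR 0.75, 118 deaths | 72% | 20% → 32% |
| 45.8% | HR 0.65, 112 deaths | 74% | 45% → 59% |
| 30% | no effect | 68% | – |
| 30% | HR 0.75, 60 deaths | 69% | 10% → 17% |
| 30% | HR 0.75, 118 deaths | 71% | 20% → 31% |
| 30% | HR 0.65, 112 deaths | 73% | 45% → 58% |
| 20% | no effect | 65% | – |
| 20% | HR 0.75, 60 deaths | 65% | 10% → 13% |
| 20% | HR 0.75, 118 deaths | 66% | 20% → 25% |
| 20% | HR 0.65, 112 deaths | 67% | 45% → 51% |

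**5. Error.** Under the global null both procedures make a false rejection exactly when the smallest p-value is at most 0.0167, so their family-wise error is identical (4.8 to 5.0% in repeated runs). If OS alone is null and the 45.8% CR rate holds, the OS false-positive rate rises from about 1.7% to 4.3% under Holm, still within the 5% limit.

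**The case against.** Bonferroni is valid, pre-specified, and applied alike to p-values and intervals. Preferring a simple method that keeps tests and intervals at the same level is defensible, especially for exploratory endpoints where the estimates matter most. All of this stands: the point is one of efficiency, and Holm does give up some of that coherence.

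Four stronger readings are tempting, and the documents do not support them.

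- *CR is sure to be significant, so ORR and OS would always be tested at 0.025 or better.* This takes 45.8% v 13.9% as a planning rate. It is retrospective background; the sample size rests on PFS alone. At the 30% rate in the same section CR power is 0.85, and at an assumed 20% it is 0.16.
- *The gain comes from CR being part of ORR.* The plan does define them so ("Secondary endpoints include objective response rate (CR+PR) and complete response rate (CR"), but Holm needs no assumption about dependence and the nesting does not produce the gain.
- *The trial's claims depend on this choice.* Section 14.4 calls the tests hypothesis-generating and excludes labeling claims whatever PFS shows.
- *Holm would make OS well powered.* With 60 deaths and HR 0.75, power goes from 10% to 18%, inadequate under either method.

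**Conclusion.** The point holds as a cheap improvement; nothing in section 14.4 is wrong. Holm gives the same family-wise protection and never rejects less. At 153 per arm the ORR gain is about 5 to 10 points with the section 3.8 case-matched rates (64% to 69–74%), about the same with the 30% phase II CR rate (64% to 68–73%), and about 1 to 4 points if BiRd CR is only 20%. OS gains about 7 to 14 points at the two section 3.8 CR rates and about 3 to 6 points at 20%.

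The ORR figures rest on retrospective ORR rates that may be optimistic. The OS figures rest wholly on assumed deaths and hazard ratios. The practical effect is limited to which secondary comparisons are reported as significant.

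**What to change.** In section 14.4, replace the Bonferroni wording for the p-values by:

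> P-values for ORR, CR and OS will be adjusted by the Holm step-down procedure (family-wise two-sided alpha 0.05); confidence intervals remain Bonferroni-corrected and are conservative, so an interval may include no difference when the Holm-adjusted p-value is below 0.05.

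Make the change before comparative outcome data are seen. It needs no more patients, data or follow-up, leaves the PFS analysis untouched, and is a standard software option. The one downside is the occasional mismatch named in the text. It can arise only for intervals on a treatment contrast. Section 14.4 describes the ORR intervals as per group and does not say whether contrasts will also be given, so the same edit should state which intervals are meant.

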4. Pregnancy test for females of child-bearing potential (FCBP). A female of childbearing potential is a sexually mature woman who: 1) has not undergone a hysterectomy or bilateral oophorectomy; or 2) has not been naturally postmenopausal (amenorrhea following cancer therapy does not rule out childbearing potential) for at least 24 consecutive months (i.e., has had menses at any time in the preceding 24 consecutive months). Pregnancy tests must occur within 10 – 14 days and again within 24 hours prior to prescribing lenalidomide (prescriptions must be filled within 7 days). FCBP with regular or no menstruation must have a pregnancy test weekly for the first 28 days and then every 28 days while on therapy (including breaks in therapy), at discontinuation of lenalidomide (whichever comes later) and at Day 28 post the last dose of lenalidomide (whichever comes later). FCBP with irregular menstruation must have a pregnancy test weekly for the first 28 days and then every 14 days while on therapy (including breaks in therapy), at discontinuation of lenalidomide (whichever comes later) and at Day 14 and Day 28 post the last dose of lenalidomide (whichever comes later) (see Appendix III: Risks of Fetal Exposure, Pregnancy Testing Guidelines and Acceptable Birth Control Methods).
5. Lenalidomide must be prescribed through and in compliance with Celgene's RevAssist® program. Prescriptions of lenalidomide must be filled within 7 days.
6. To occur within 6 weeks of treatment
7. Iliac crest bone marrow aspirate for cytological review, including cytogenetics, FISH studies, flow cytometry (when available), and core biopsy for immunohistochemistry.
8. To confirm complete remission, progression, or when clinically indicated
9. An additional safety assessment will be done 30 days (+/- 7 days) following the last dose of study drug.

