MRD: Minimal residual disease testing will be performed in subjects who achieve complete response. MRD testing may be performed either by flow cytometry or PCR, whichever is more readily available at the study institution.

Subjects will continue their randomized treatment assignment until disease progression or unacceptable toxicity (whichever occurs first). In case toxicity precludes dosing of one agent (i.e dexamethasone, clarithromycin, lenalidomide), treatment regimen will continue with the remaining agents. Subjects unable to receive ALL the components of the assigned treatment arms will be removed from study after reasonable attempts to dose reduce and manage side effects. Subjects with elevations of AST/ALT greater than three times the upper limit of normal, with concomitant elevation of bilirubin 2 times the upper limit of normal, not attributable to disease, should be discontinued from treatment. Subjects can also be removed from study at investigator's discretion, or if they withdraw consent. At completion or early discontinuation of treatment, subjects will be followed for 30 additional days or up to the initiation of subsequent treatment (whichever occurs first), after which they will be off the active treatment phase of the study. Long term follow up for disease status and survival will proceed until the subject has withdrawn consent, is lost to follow up, or has died.

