14.0 STATISTICAL CONSIDERATIONS

14.1 Study Design/Primary Endpoint

The study is a randomized phase III design, and the primary endpoint in both treatment arms is median PFS. PFS will be defined as the time from randomization day until objective progression or death from any cause. The PFS distributions of the two treatment arms will be estimated by Kaplan-Meier survival analysis and the PFS distributions will be compared by an unstratified log-rank test. Ninety-five percent confidence intervals for the Kaplan-Meier PFS estimates will be calculated using

Greenwood's formulae. The primary comparison will be made using the intent-to-treat (ITT) patient population. Patients will be analyzed based on their randomization assignments, regardless of therapy initiation or compliance. A secondary analysis will be performed comparing "evaluable" patients as patients who met eligibility requirements, have initiated therapy, and were not removed from the study for non-compliance or patient withdrawal.

The median PFS for MM patients receiving Revlimid /dexamethasone chemotherapy (Rd) (Arm A) is expected to be approximately 25.5 months, as reported in the MM-010 study of continuous Rd vs Rd for 18 months (Facon T, Dimopoulos M, Dispenzieri A, et al: Initial phase 3 results of the FIRST trial in newly diagnosed multiple myeloma patients ineligible for stem cell transplant. 2013 ASH Annual Meeting. Abstract 2. Presented December 8, 2013.). Therefore, the target median PFS for patients receiving Revlimid/dexamethasone/Clarithromycin (BiRd) (Arm B) is hypothesized to be 44.6 months (target hazard ratio = 1.75).

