14.2 Sample Size/Accrual Rate

To achieve 90% power to detect a 75% increase in median PFS (44.6 vs. 25.5 months), at the two-sided 0.05 significance level, will require 306 patients total, accrued over approximately 3.0 years (assuming an accrual rate of approximately 9 patients/month), with an additional 12 months of follow-up subsequent to termination of accrual.

When the sample size in each group is 153 patients, with a total number of PFS events required of 133, an exponential maximum likelihood test of equality of survival curves with a 0.05 two-sided significance level will have 90% power to detect the difference between an Arm A (Rd) median PFS of 25.5 months and an Arm B (BiRd) median PFS of 44.6 months (a constant hazard ratio of 1.75); this assumes an accrual period of 3.0 years, a maximum follow-up time of 4.0 years, and no dropouts. The exponential assumption is for planning purposes only, actual analysis will employ nonparametric methods for estimation and testing of survival distributions. Assuming a 10% dropout rate, approximately 337 patients will be accrued to the study.

A futility analysis will be conducted after 50% of the total PFS events required for final analysis has occurred (i.e., 66 of the 133 required PFS events). No accrual suspension is required to conduct the futility analysis. If at this point (i.e., after accumulation of 66 PFS events) the hazard ratio of the control arm over the experimental arm is 1.0 or less, the study will be stopped for futility.

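### Section 14.4 reports toxicity only as crude proportions, although treatment runs to progression and BiRd is hypothesised to delay it; add time on treatment and event rates by treatment-time window

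*Combined protocol and SAP*

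**What the plan says.** Section 14.4 (Analysis of Secondary Endpoints) gives the toxicity analysis in two statements, apart from naming the grading system: "The frequency of subjects experiencing toxicities will be tabulated", and "Exact 95% confidence intervals around the toxicity proportions will be calculated to assess the precision of the obtained estimates". It plans no rate per patient-time, no time to first event and no summary within a fixed window, and it assigns no between-arm test to toxicity.

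Section 4.1 sets the duration of treatment: "Subjects will continue their randomized treatment assignment until disease progression or unacceptable toxicity (whichever occurs first". Footnote 9 of the Schedule of Assessments (Section 1.3) adds: "An additional safety assessment will be done 30 days (+/- 7 days) following the last dose of study drug". Routine observation for toxicity therefore follows time on treatment, plus about a month.

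Section 14.2 gives the design hypothesis: "To achieve 90% power to detect a 75% increase in median PFS (44.6 vs. 25.5 months), at the two-sided 0.05 significance level". It assumes three years of accrual and a maximum follow-up of four years.

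Two nearby items do not fill the gap. Relative dose intensity (Section 4.1) is a per-cycle dose ratio. The comparison of follow-up adequacy in Section 14.3 concerns PFS.

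**The concern.** A binomial proportion has a like-for-like meaning between arms when patients are observed for similar lengths of time. Here time at risk ends at progression in both arms, and the trial is built on the expectation that progression comes later on BiRd. If so, equal monthly risk would appear as a somewhat higher percentage on BiRd. The exact interval would not reveal this, because it conveys sampling error only. If BiRd patients instead stopped early, the distortion would run the other way.

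Objective 2.1.5 is to assess safety in each arm, and Section 3.8 anticipates less toxicity with the combination. A moderate true reduction in monthly risk could be hidden in the planned table.

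**Working it through.** **Inputs from the documents.** Median PFS 25.5 months (Rd) and 44.6 months (BiRd); 36 months of accrual; data cut at 48 months, so follow-up T is uniform on 12 to 48 months; 153 patients per arm; 133 PFS events; exponential PFS for planning.

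**Assumptions, not in the documents.** A constant monthly hazard h of first toxicity, equal in both arms; other discontinuation at d per month, equal in both arms, with d from 0 to 0.03.

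**Step 1. The plan's own figures.** 44.6/25.5 = 1.749, as stated. The Schoenfeld event count is 4 × (1.960 + 1.282)² / (ln 1.75)² = 134.2, rounded up to 135, against 133 stated; power at 133 events is 0.897. An exponential log-hazard calculation gives 154.5 patients per arm against 153. The PFS inputs are sound and are used as they stand.

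**Step 2. Time on treatment at the cut.** The progression hazards are λ = ln 2/25.5 = 0.02718 (Rd) and ln 2/44.6 = 0.01554 (BiRd). Let M(L) = [exp(−12L) − exp(−48L)]/(36L), the mean of exp(−LT). Mean time on treatment is [1 − M(λ)]/λ.
- Rd: (1 − 0.4603)/0.02718 = 19.9 months.
- BiRd: (1 − 0.6356)/0.01554 = 23.4 months.
- Ratio 1.18. Replacing λ by λ + d gives 1.17, 1.15 and 1.14 for d = 0.01, 0.02 and 0.03.

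**Step 3. Crude proportions under equal risk.** With L = h + λ + d, the proportion is (h/L) × [1 − M(L)].

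| h per month | d | Rd | BiRd | Excess (points) |
|---|---|---|---|---|
| 0.01 | 0 | 17.4% | 20.3% | 2.9 |
| 0.02 | 0 | 30.8% | 35.5% | 4.7 |
| 0.02 | 0.01 | 27.5% | 31.4% | 3.9 |
| 0.02 | 0.03 | 22.4% | 25.2% | 2.7 |

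The last excess is taken before rounding. Over h from 0.0025 to 0.10 and d from 0 to 0.03, the excess runs from 0.5 to 6.8 points. For scale, the exact 95% CI for 47/153 is 23.5% to 38.7%.

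**Step 4. Masking.** A true 15% reduction on BiRd (0.017 against 0.020 per month, d = 0) would appear as 31.4% (BiRd) against 30.8% (Rd).

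**Step 5. Early toxicity.** Put equal risk of 0.05 per month in months 0 to 6 only. The proportion is h/(h + λ) × [1 − exp(−6(h + λ))], which gives 24.0% (Rd) and 24.8% (BiRd). The crude table is then nearly unbiased.

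**Step 6. Candidate additions.**
- *Whole-treatment rate, constant hazard.* Mean event-free time on treatment at h = 0.02 is 15.4 and 17.8 months. The rates are 0.3081/15.41 = 0.020 and 0.3555/17.77 = 0.020, so the ratio is 1.00.
- *Whole-treatment rate, early risk as in Step 5.* Mean event-free time is 15.4 and 18.1 months. The rates per 100 months are 24.0/15.4 = 1.56 and 24.8/18.1 = 1.37, a ratio of 0.88 (0.89 if 30 days after the last dose are added). Equal risk now looks like an advantage for BiRd.
- *Cumulative incidence with end of treatment as competing event.* Under constant risk this is h/(h + λ) × [1 − exp(−(h + λ)t)]. With h = 0.02 at 48 months it is 38.0% against 46.1%, a gap of 8.1 points, which is larger than the crude gap of 4.7.
- *Rates within treatment-time windows.* With equal constant risk inside a window, each arm's rate equals h whatever the treatment length. The early-risk case is therefore handled by the 0 to 6 month window.

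**Step 7. Precision in the last window.** With h = 0.02, d = 0 and L = h + λ, the expected first events after month 24 per 153 patients are 153 × h × exp(−24L) × [24/L − (1 − exp(−24L))/L²]/36. That is about 5.6 (Rd) and 8.0 (BiRd), so late-window ratios will be imprecise.

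**The case against.** The strongest objection is that the plan makes no comparative toxicity claim. Objective 2.1.5 speaks of assessment in each arm, whereas several efficacy objectives speak of comparison. Section 14.4 presents the intervals as statements of precision and assigns tests elsewhere. As a within-arm description, the crude proportion is valid: it says how many patients had the toxicity. This stands, and it is why the crude table should stay.

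The assumptions also matter. No toxicity hazard is given in the documents. Treatment also ends for toxicity, long cycle delays, non-compliance, withdrawal or investigator decision (Sections 4.1, 9.5 and 10.11), which narrows the exposure gap. Section 9.1 moves some patients to a maintenance regimen that does not list clarithromycin, while Section 4.1 keeps patients on their randomised assignment. Those passages must be reconciled, and until then the extra BiRd months cannot all be read as three-drug exposure.

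Some safety review does have a time frame: the 30-day criteria in Section 9.2 and the six-monthly DSMB review in Section 13.2. Second primary malignancies are collected until all patients have at least five years from randomisation or have died (Section 11.2), so their ascertainment does not stop with treatment.

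A reader might infer from the 75% difference in medians that BiRd exposure would be 75% longer. That holds only if everyone is followed to progression, where equal hazards of 1% and 2% per month would give 26.9% against 39.2% and 42.4% against 56.3%. The documents describe no such safety analysis. A reader might also infer a high risk of a falsely significant toxicity difference. At 2% per month a 5%-level test would reject in about 14% of trials, but the plan contains no such test.

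**Conclusion.** The point holds as a cheap improvement. The planned toxicity summary takes no account of time at risk, in a design where success would make time at risk differ between arms. At the planned cut the difference in mean time on treatment is about 18%, or 14 to 17% with other discontinuation of 1 to 3% per month. With progression the only reason to stop, the resulting excess in BiRd crude proportions is about 3 to 5 points at an assumed equal, constant hazard of 1 to 2% per month. It is about 1 point or less in the early-onset case at 5% per month. All of this depends on BiRd prolonging PFS as hypothesised, and the hazards are assumptions.

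The documents do not support saying that the planned tables would seriously misstate BiRd's harm: the excess lies within one arm's exact interval. Nor should whole-treatment rates or cumulative incidence replace the crude table as the sole basis for comparing arms. Step 6 shows that the former can favour the longer-treated arm and that the latter also depends on treatment length.

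**What to change.** Keep the crude table with exact intervals. Add to Section 14.4, by arm:

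1. Median and total time on treatment.
2. First-event incidence per 100 patient-months at risk, counted from first dose to the earliest of first event, 30 days after last dose, or data cut, with the BiRd:Rd rate ratio and 95% CI. State how last dose is defined when one drug stops and the others continue.
3. The same rates within fixed treatment-time windows, for example months 0–6, 6–12, 12–24 and over 24.

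State that between-arm toxicity will be interpreted from the windowed rates together with the crude table, and that any cumulative incidence curve with end of treatment as a competing event is descriptive only.

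The cost is a paragraph and a few tables. Drug diaries (Section 10.5) and adverse event records (Section 11.1) already exist; the team should confirm that onset dates are captured. Sample size, visits and treatment are unchanged. The downside is more output and imprecise late-window rates, which should be presented as such.
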